7.2 Subject Exclusion Criteria

Subjects must NOT meet any of the following exclusion criteria to qualify for the study:

1. Any of the following forms of invasive candidiasis at baseline:
 - a. Septic arthritis in a prosthetic joint (septic arthritis in a native joint is allowed)
 - b. Osteomyelitis
 - c. Endocarditis or myocarditis
 - d. Meningitis, endophthalmitis, chorioretinitis, or any central nervous system infection
 - e. Chronic disseminated candidiasis
 - f. Urinary tract candidiasis due to ascending *Candida* infection secondary to obstruction or surgical instrumentation of the urinary tract
2. Received systemic treatment with an antifungal agent at approved doses for treatment of candidemia for > 48 hours (e.g., > 2 doses of a once daily antifungal agent or > 4 doses of a twice daily antifungal agent) ≤ 4 days (96 hours) before randomization.
 - a. Exception: Receipt of antifungal therapy to which any *Candida* spp. isolated in culture is not susceptible (see [Appendix 1](#))
3. Alanine aminotransferase or aspartate aminotransferase levels > 10 -fold the upper limit of normal (ULN).
4. Severe hepatic impairment in subjects with a history of chronic cirrhosis (Child-Pugh score > 9).

5. Presence of an indwelling vascular catheter or device that cannot be removed or an abscess that cannot be drained and is likely to be the source of candidemia or invasive candidiasis.
6. Known hypersensitivity to Rezafungin for Injection, caspofungin, any echinocandin, or to any of their excipients, including but not limited to hereditary sugar disorders (e.g., fructose intolerance, sucrose-isomaltase insufficiency), anaphylaxis, or echinocandin-induced exfoliative skin disorders (e.g., Stevens-Johnson syndrome or toxic epidermal necrolysis).
7. Meets National Cancer Institute Common Terminology Criteria for Adverse Events (CTCAE) version 5.0, criteria for ataxia, tremor, motor neuropathy, or sensory neuropathy of Grade 2 or higher.
8. History of severe ataxia, tremor, or neuropathy or a diagnosis of multiple sclerosis or a movement disorder (including Parkinson's Disease or Huntington's Disease).
9. Planned or ongoing therapy at Screening with a known severe neurotoxic medication (see [Appendix 9](#)) or with a known moderate neurotoxic medication (see [Appendix 9](#)) in a patient with ataxia, tremor, motor neuropathy, or sensory neuropathy of CTCAE version 5.0 Grade 1 or higher.
10. Previous participation in this or any previous rezafungin study.
11. Current participation in another interventional treatment trial with an investigational agent.
12. Recent use of an investigational medicinal product within 28 days of the first dose of study drug or presence of an investigational device at the time of Screening.
13. Pregnant or lactating females.
14. The Principal Investigator (PI) is of the opinion the subject should not participate in the study.

7.3 Requalification for Entry

Subjects not fulfilling the entry criteria and not randomized may be rescreened for participation if their eligibility characteristics have changed.

7.4 Subject Withdrawal Criteria

7.4.1 Withdrawal from Study Protocol

Subjects may withdraw consent to participate in this study at any time without penalty or loss of benefits to which the subject is otherwise entitled. Subjects on study drug who wish to withdraw completely from this clinical study should be encouraged to complete the assessments at EOT. Every reasonable effort should be made to determine the reason a subject withdraws prematurely, and this information should be recorded on the appropriate page(s) of the electronic case report form (eCRF).

Subjects may be withdrawn from the study for any of the following reasons:

- Subject unable or unwilling to continue
- Subject elects to withdraw informed consent
- AE (whether related to study drug or not) that precludes further participation in the study in the judgment of the PI and/or Sponsor
- Protocol non-compliance
- Subject lost to follow up
- The PI considers that it is in the subject's best interest not to continue participation in the study

Subjects withdrawn from the study may refuse to participate in the Follow-up visit; however, every effort should be made to collect survival data and safety assessments on Day 30 (-2 days) for all subjects who withdraw for reasons other than withdrawal of informed consent. Following enrollment, subjects diagnosed with invasive candidiasis involving one or more organ systems and normally excluded from study participation (Exclusion Criterion 1, [Section 7.2](#)) do not need to exit the study. Documentation of the disease should be placed in the eCRF along with any further interventions related to the disease.

7.4.2 Early Discontinuation from Study Drug Administration

For subjects who prematurely discontinue study drug (i.e., before the anticipated full course of study drug therapy required for effective treatment of candidemia and/or invasive candidiasis), EOT assessments should be performed on the day of discontinuation. For premature study drug discontinuation, Day 14 efficacy assessments should also be performed at EOT, except when the subject is believed to be a clinical cure, then the efficacy assessments should still be performed at the Day 14 visit to ensure there is no relapse between EOT and Day 14. All safety assessments and assessment of mortality should be done for subjects who discontinue study drug early. The reason for premature discontinuation of study drug administration should be recorded on the appropriate page(s) of the eCRF. Reasons for withdrawal from study drug may include, but are not limited to:

- Cultures negative for *Candida* spp.
 - Blood culture is positive for yeast at enrollment, but the final local blood culture results conclude the yeast is not *Candida* spp.
 - Subject is enrolled based on a rapid IVD test positive for *Candida* spp., but final local blood culture results from Screening or tissue/fluid culture results from a normally sterile site are negative for *Candida* spp. (withdrawal not required but based on the Investigator's discretion)

- Safety
 - Subject unable or unwilling to continue or informed consent withdrawn
 - Occurrence of an AE that, in the opinion of the Investigator, warrants the subject's permanent discontinuation from study drug therapy. This includes development of a clinically significant laboratory abnormality that requires discontinuation from study drug (IV and IV/oral) therapy. In the event of discontinuation from study drug therapy due to the occurrence of an AE, the study site should notify the Medical Monitor as soon as possible
 - Suspected or confirmed pregnancy or nursing during the study drug administration period
- Excluded types of invasive candidiasis

Echinocandins are not appropriate therapy for *Candida* infections of the eye or central nervous system due to low drug distribution to these sites (Pappas 2016; Cornely 2012). A retinal examination for evidence of a *Candida* eye infection, including endophthalmitis or chorioretinitis, should be performed in all subjects with candidemia during Screening when possible, although may occur as late as Day 7 only on subjects with candidemia by blood culture, and should be repeated in subjects who were negative at baseline if the subject develops visual signs or symptoms of a *Candida* eye infection during the study. Additionally, any neutropenic subjects who recover their neutrophil counts during the study should have an additional retinal examination. Subjects who were negative at baseline and diagnosed with a *Candida* eye infection after initiating study drug should have an urgent ophthalmologic consultation (if not already done), should stop study drug, and be initiated on appropriate therapy for *Candida* eye infection per the local guidelines. If possible, all subjects diagnosed with endophthalmitis or chorioretinitis should remain in the study and all subsequent antifungal drugs, interventions, and outcomes for endophthalmitis or chorioretinitis should be recorded.

Study drug may be continued in the event of diagnosis of other forms of invasive candidiasis listed in the exclusion criteria if the involvement of other organ systems was thought to be present at the time of enrollment and the diagnosis was delayed. If, on the other hand, the spread of *Candida* infection to other organ systems was thought to have occurred following enrollment and initiation of study drug, the Investigator should consider a change of therapy due to insufficient therapeutic effect of study drug. In all cases of other forms of invasive candidiasis, the Investigator should consult local guidelines for the most appropriate management of disease and whether or not additional antifungal therapy may be warranted either during study drug administration or following completion of study drug therapy.

- Insufficient therapeutic effect

An insufficient therapeutic effect may be determined prior to the planned duration of therapy in the study. This determination will require an assessment of clinical status including the synthesis of symptoms and signs data (both local and systemic). Subjects who are deemed to have an insufficient therapeutic effect should be discontinued from study drug therapy.

If a subject has daily blood cultures positive for *Candida* spp. through Day 7 despite appropriate study drug administration, this should be considered an insufficient therapeutic effect and study drug should be discontinued and salvage therapy initiated. The subject should remain in the study through the Follow-up visit (Days 52–59) to complete safety assessments and assess for mortality.

Seven days is the maximum number of daily positive blood cultures allowed prior to a change in antifungal therapy. The Investigator may determine that there is an insufficient therapeutic response prior to Day 7.

- Investigator discretion
 - Resistant Pathogen(s): In the event an organism resistant to ≥ 1 of the potential study drugs is isolated, the Investigator will determine whether the subject remains on study drug therapy. The Investigator may decide to continue study drug therapy if, in the Investigator's opinion, there is clear and continuing clinical improvement while on therapy.
 - The Investigator may decide to prematurely discontinue study drug therapy and to initiate an alternative and appropriate therapy if, in the Investigator's opinion, the subject is not benefiting from study drug.

NOTE: The Medical Monitor should be contacted to discuss whether to continue or prematurely discontinue a subject on the study drug in the event the subject requires systemic concomitant antifungal therapy.

In the event salvage therapy is required due to either insufficient therapeutic effect or Investigator discretion, the Investigator should note that since the subject has failed echinocandin therapy, other echinocandins may not be the best choice for salvage therapy. If the subject is switched to oral step-down therapy prior to study drug failure, the Investigator should consider that subjects in the caspofungin arm will also have been taking fluconazole. In both circumstances, the Investigator should refer to the IDSA ([Pappas 2016](#)) or ESCMID ([Cornely 2012](#); [Ullmann 2012](#)) guidelines for treatment failure in candidemia, and will need to determine whether or not breaking the blind is necessary to make an informed choice of future antifungal therapies.

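### The stop rule for Candida eye infection omits subjects whose first retinal examination is positive after dosing, and CNS infection has no explicit stop rule

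*Protocol*

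**What the plan says.** Protocol 7.4.2, under excluded types of invasive candidiasis, opens with a rationale: echinocandins are not suitable treatment for Candida "infections of the eye or central nervous system due to low drug distribution to these sites". The rationale names both sites and does not depend on any baseline finding.

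The instruction that follows is limited. It applies to "Subjects who were negative at baseline and diagnosed with a" Candida eye infection once study drug has started. Those subjects "should stop study drug, and be initiated on appropriate therapy for" that infection under local guidelines.

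The next paragraph covers the remaining excluded forms. It says "Study drug may be continued in the event of diagnosis of other forms of invasive candidiasis listed in the exclusion criteria". The condition is that the infection is judged to have existed already at entry and was merely recognized late. Where spread is thought to have followed enrollment, "the Investigator should consider a change of therapy due to insufficient therapeutic effect of study drug". For all such forms, "the Investigator should consult local guidelines for the most appropriate management of disease".

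Three other parts of the Protocol matter here:

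- Section 6.1.5 asks for the retinal examination at Screening where possible in subjects with candidemia, but accepts it up to Day 7.
- Exclusion criterion 1d (Section 7.2) covers eye infection and any CNS infection.
- Section 7.4.1 foresees excluded forms being found after enrollment and lets those subjects stay in the study.

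**The concern.** A stop rule should be at least as wide as the reason given for it. Here the reason is poor drug penetration at two sites. That applies to every subject, since both arms start on an echinocandin, whatever a baseline examination showed. The rule covers one of the two sites, and only subjects with a negative baseline result.

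The omitted eye case arises on a route that the Protocol itself provides, the deferred first examination. At stake is delay in changing treatment for an infection of the eye or CNS in a subject on a drug that the Protocol calls unsuitable for that site. This is a matter of patient safety and clear site instructions. It does not concern the statistical design.

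**Working it through.** No calculation applies. The check sets the relevant texts side by side and counts where the limited sentence appears.

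**Where the limited stop sentence appears in the Protocol.** Synopsis (1), Table 1 footnote q (1), Section 6.1.5 (1), Section 7.4.2 (1), and the on-treatment visit sections 9.2.1 to 9.2.8 (8) and 9.4.1 to 9.4.4 (4). That is 1 + 1 + 1 + 1 + 8 + 4 = 16. SAP Appendix 2 footnote q reproduces it once more, making 17. None of the 17 names CNS infection. Section 7.4.2 uses should for stopping; the other 16 use must.

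**Eye infection.**

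1. Section 6.1.6 defines Day 1 as the first dosing day, so an examination on Days 2 to 7 follows the first dose.
2. Sections 9.2.2 to 9.2.5 (Day 2, Day 3, Day 4, Days 5–7) each order the examination if it was not done at Screening. These are 4 sections where a first examination necessarily follows dosing. Section 9.2.1 (Day 1) is a fifth if the examination comes after the infusion.
3. Suppose that examination is positive. If it counts as the baseline examination, the subject was positive at baseline. If it does not, there is no baseline result. In neither case was the subject negative at baseline.
4. A looser reading would take the phrase to mean no known eye infection at entry. But Section 7.4.2 uses the same phrase to say whose examination is repeated, which points to an examination result.

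On the most natural reading, then, this subject is outside the rule.

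**CNS infection.** The continuation paragraph refers to other forms on the exclusion list without saying other than what.

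- If it means other than eye, a CNS infection already present at enrollment but diagnosed late falls under the permission to continue, against the section's opening statement.
- If it means other than eye and CNS, which is the more natural reading, CNS infection has the opening statement but no instruction.

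Either way there is no explicit stop.

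**What the remaining text does.**

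- Excluded types of candidiasis appear as a reason for stopping, but on a permissive list: "Reasons for withdrawal from study drug may include, but are not limited to".
- Insufficient therapeutic effect does call for discontinuation, but the judgment rests on clinical status, signs and symptoms. The first retinal examination is routine in candidemia, so a positive result may come without symptoms.
- Section 7.4.2 allows stopping at the Investigator's discretion and asks for Medical Monitor contact when other systemic antifungals are needed. Section 8.5 restricts such drugs.

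These provisions permit stopping or point toward it. None requires it because of the infection site.

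**The case against.** The strongest answer is that nothing in the Protocol tells a site to keep dosing a subject with eye infection, and that the section's opening statement already says what is needed for both sites. Several features support this:

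- The section lists excluded types of candidiasis among reasons to stop.
- The sentence after the eye instruction, which has no baseline limit, asks that all subjects with endophthalmitis or chorioretinitis stay in the study where possible and have later antifungal treatment recorded. It evidently expects other treatment.
- In the Day 1 to Days 5–7 visit sections the stop sentence shares a bullet with the deferred first examination, so a site would probably apply it to that result.
- For CNS infection, the natural reading of the continuation paragraph leaves it out.

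Most of this stands, and it is why the severity is low. It shows that the intent is probably to stop. It does not put the two omitted cases into the operative wording, and it leaves them to judgment where the plan gave baseline-negative eye infection an instruction.

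A reader might infer more: that the Protocol directs continued echinocandin treatment for eye or CNS infection, or that the efficacy results are compromised. The documents support neither. The first depends on one reading of an ambiguous phrase, and only for late-diagnosed CNS infection. On the second, SAP Table 2-3 already counts new antifungal therapy for Candida endophthalmitis or chorioretinitis as mycological failure, and Day 30 mortality is counted irrespective of intercurrent events (SAP Table 2-1).

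Timing also limits the value. SAP 1.2.2 dates the last primary-enrollment randomization to 16 August 2021. With dosing the same day, Day 59 is 58 days later, 13 October 2021, before SAP V4.0 of 2 November 2021. By then only the China extension could benefit, under a country amendment not among these documents.

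**Conclusion.** The point holds as a wording defect of low severity. The stop instruction is narrower than its own rationale in two respects: eye infection found at a first retinal examination after dosing, and CNS infection. The eye part rests on reading the baseline phrase as an examination result, which the repeat-examination wording favors but does not settle. The CNS part holds on either reading of the continuation paragraph, as absence of an explicit stop rather than as permission to continue.

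Few subjects are likely to be affected. The eye case needs candidemia, no Screening examination, and a positive first examination after dosing; the documents give no rate for this. Endpoints, sample size, power and alpha do not change.

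**What to change.** 1. In Section 7.4.2, and wherever the sentence is copied in the Protocol (16 places in all), remove the baseline limit. Suggested wording: *Any subject diagnosed with a Candida eye infection after initiating study drug, including at a first retinal examination performed after dosing*. Keep the ophthalmology consultation and local-guideline treatment in 7.4.2.
2. In Section 7.4.2, add that study drug is to be stopped and appropriate therapy started for CNS Candida infection diagnosed after the first dose.
3. In the same section, limit the continuation paragraph to excluded forms other than eye or CNS infection.

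Aligning should with must in 7.4.2 and updating the SAP footnote are optional housekeeping.

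The cost is a short wording amendment with notice to sites, and slightly less Investigator discretion for CNS infection. No visits, procedures or subjects are added.

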7.5 Replacement of Subjects

Randomized subjects who are withdrawn will not be replaced.

7.6 Study Termination by Sponsor and Termination Criteria

The Sponsor reserves the right to terminate an investigational site or this clinical study at any time. Reasons for termination may include, but are not limited to, the following:

- The incidence or severity of AEs in this or other studies of Rezafungin for Injection indicate a potential health hazard to subjects
- Serious or persistent noncompliance by the Investigator with the protocol, clinical research agreement, or applicable regulatory guidelines in conducting the study
- IRB/IEC decision to terminate or suspend approval for the investigation or the Investigator
- Investigator request to withdraw from participation
- Subject enrollment is unsatisfactory

8.0 STUDY DRUGS

Subjects will be randomized in a 1:1 ratio to receive Rezafungin for Injection IV or Caspofungin IV. Oral step-down therapy is allowed in both treatment groups; oral placebo in the Rezafungin for Injection group and oral fluconazole in the Caspofungin group. The total IV plus oral treatment duration will be ≥ 14 days and up to a maximum of 28 days (Table 3).

In order to stop study drug for successful completion of therapy prior to 28 days, the following criteria must be met:

- ≥ 14 days of study drug
- The subject's clinical status is considered stable based on Investigator assessment
- All systemic signs attributable to candidemia and/or invasive candidiasis that were present at baseline have resolved
- For subjects with invasive candidiasis, there is documented or presumed eradication of invasive candidiasis
- If a blood culture is positive at Screening, the most recent post-baseline blood culture is negative for *Candida* spp.

Once these criteria are met, the total duration of study drug is at the discretion of the PI.

Subjects randomized to the Rezafungin for Injection treatment group will receive 1 dose of Rezafungin for Injection IV (400 mg) nominally over 60 (± 10) minutes on Day 1 and 200 mg on Day 8 (± 1 day) (Table 3). Subjects in the Rezafungin for Injection treatment group who require >14 days of therapy will receive an optional third dose of Rezafungin for Injection IV (200 mg) on Day 15. Subjects in the Rezafungin for Injection treatment group who require >21 days of therapy will receive an optional fourth dose of Rezafungin IV (200 mg) on Day 22. Subjects in the Rezafungin for Injection treatment group will receive IV or oral placebo on other study days in order to maintain the blind. Intravenous study drug is administered 24 (± 2) hours after study drug was administered on the previous day.

Subjects may receive oral step-down therapy after ≥ 3 days of IV therapy or the minimum duration of IV therapy advised by the site's national/regional/local guidelines, whichever is greater. Step-down therapy in the Rezafungin for Injection treatment group will be oral placebo, in order to maintain the blind. Subjects who have already switched to oral step-down therapy will receive both oral placebo and Rezafungin for Injection IV on Day 8 (± 1 day), Day 15 (± 1 day) for subjects who require >14 days of therapy, and Day 22 (± 1 day) for subjects who require >21 days of therapy.

Subjects randomized to the caspofungin group will receive IV caspofungin (a single 70 mg loading dose on Day 1 followed by 50 mg once daily over 60 (± 10) minutes) for ≥ 3 days and up to a maximum of 28 days (Table 3). Intravenous study drug is administered 24 (± 2) hours after study drug was administered on the previous day.

Step-down therapy in the caspofungin treatment group will be oral fluconazole (subjects with a creatinine clearance >50 mL/min will receive oral fluconazole at a dose of 6 mg/kg administered once daily rounded to the nearest 200 mg increment with a maximum daily dose of 800 mg; subjects with creatinine clearance ≤ 50 mL/min will receive oral fluconazole at a dose of 3 mg/kg administered once daily rounded to the nearest 200 mg increment with a maximum daily dose of 400 mg). In order to maintain the blind, subjects who have already switched to oral step-down therapy will receive both oral fluconazole and IV placebo on Day 8 (± 1 day), Day 15 (± 1 day) for subjects who require >14 days of therapy, and Day 22 (± 1 day) for subjects who require >21 days of therapy.

Intravenous infusion of Rezafungin for Injection and IV placebo is administered over 60 (± 10) minutes, although the infusion time may be increased up to 180 minutes to manage evolving symptoms of infusion reaction consistent with management of echinocandin class infusion reactions, whereby decreasing the rate of infusion often alleviates symptoms. Dosage adjustments of Rezafungin for Injection are not allowed. Treatment will be initiated on an inpatient basis; a switch to outpatient IV treatment is allowed at the Investigator's discretion.

The total IV plus oral treatment duration will be ≥ 14 days and up to 28 days.

The daily dosing schedule with options (i.e., not switched versus switched to oral therapy) for the required treatment period is presented in [Figure 2](#) and for the optional treatment period is in [Figure 3](#). The daily dosing schedule for the entire study period (required and optional) with options (i.e., not switched versus switched to oral therapy) is presented in [Table 3](#).

